4.2 Exclusion Criteria

(1) Age <18 years.

(2) Women planning to become pregnant, already pregnant, or breastfeeding.

(3) Incomplete required data.

(4) Unable to expertly use the WeChat mini-program or unstable internet environment.

(5) Presence of red-green color blindness or other uncorrectable visual impairment.

(6) Cardiac, pulmonary, or renal failure, or unstable vital signs.

(7) Unwilling to participate in the study or unable to sign informed consent.

(8) Any other condition that may interfere with study assessments, increase subject risk, or affect study completion, deemed unsuitable by the investigator.

(9) Participation in another clinical trial within the past 3 months or currently participating in another clinical trial.

5. Study Variables

·Exposure factors: Laboratory indicators, blood ammonia, data derived from the newly developed mini-program, MELD score, presence of other diseases (hypertension, diabetes, cardiovascular disease), variables for nutrition and sarcopenia assessment, medication regimens, etc.

·Outcome indicators: Death/discharge against medical advice, liver transplantation, TIPS, hepatic encephalopathy (OHE/CHE), frailty, sarcopenia, malnutrition, decreased quality of life, etc.

·Predictors:

(1).Demographic characteristics: age, sex, education level, anthropometric data (height, weight), etc.

(2).Past medical history and comorbidities: etiology of cirrhosis (viral hepatitis,

autoimmune, alcoholic, etc.), cirrhosis complications (gastrointestinal bleeding, ascites, splenomegaly, hepatic encephalopathy, etc.), comorbidities (hypertension, diabetes, cardiovascular disease, kidney disease, psychiatric disorders; infections, etc.), whether TIPS has been performed, etc.

(3).Laboratory indicators: complete blood count, liver and kidney function, coagulation, blood ammonia, electrolytes, C-reactive protein, procalcitonin; imaging indicators; frailty/sarcopenia-related indicators: handgrip strength (dominant hand), abdominal circumference, body mass index (BMI), etc.

(4).Scores and scales: Child-Pugh class, MELD score, MELD-Na score, PHES score, quality of life (scale), data from the mini-program, etc.

(5).Lifestyle habits (smoking, alcohol consumption, etc.), nutritional intake (protein, calories, etc.), etc.

(6).Medications at baseline (anti-HE drugs, dosage, frequency; psychiatric drugs; other drugs such as diuretics, etc.), medications used at outpatient visit/discharge and their frequency, etc.

(7).Record the number, reasons, and length of stay for unplanned rehospitalizations.

(8).Confounders: Severity of liver function, age, education level, etiology of cirrhosis, medication use, prior history of HE, etc.

·Effect modifiers: Child-Pugh class, age, etiology of cirrhosis, etc.

To control selection bias, clear and unified inclusion/exclusion criteria will be used, and participants will be enrolled through consecutive recruitment rather than convenience sampling. To control information bias, tests will be administered by different personnel at different time points to ensure information isolation; testers will be trained and standardized procedures established. Questionnaires will be administered in a quiet, private environment. For confounding bias, when comparing prognoses between groups with different test results, individual matching or frequency matching for important confounders (e.g., age, liver function) may be performed. Stratified analysis of confounders will be conducted during data analysis.

6. Sample Size Determination

$$n_{\text{患病组}} = \frac{Z_{\alpha/2}^2 \times \text{Sensitivity} \times (1 - \text{Sensitivity})}{W^2}$$

$$n_{\text{非患病组}} = \frac{Z_{\alpha/2}^2 \times \text{Specificity} \times (1 - \text{Specificity})}{W^2}$$

$$N_{\text{总}} = \frac{n_{\text{患病组}}}{\text{患病率}} + \frac{n_{\text{非患病组}}}{1 - \text{患病率}}$$

Referring to the reference "Detection of minimal hepatic encephalopathy in patients with cirrhosis based on the Stroop-CN model (NCRCID-CHESS 2106): a prospective multicenter study." The specificity was 0.595, sensitivity 0.667. The proportion of HE in the cirrhotic population is 50-80%, and W was set at 0.1. At a prevalence of 50%, the sample size was 358; at 80%, the sample size was 573. According to the formula, the sample size is calculated to be 358-573 cases. Assuming a dropout rate of 15%, approximately 421-674 cases are ultimately needed.

For the healthy population, using the formula $n = \left(\frac{Z \times \sigma}{W} \right)^2$, with $Z=1.96$, $W=2$, and standard deviation=10, approximately 98 individuals are needed. This is rounded to 120 for collection, which is a common sample size for establishing normal reference values in clinical diagnostic tests.

7. Statistical Analysis Plan

Data will be processed using SPSS, R, and GraphPad Prism 9. The K-S test will be used to analyze whether data follow a normal distribution. Normally distributed continuous data will be expressed as mean \pm standard deviation ($\bar{x} \pm s$); non-normally distributed continuous data will be expressed as median and interquartile range [M (P25, P75)]. Comparisons between two groups will be performed using independent samples t-test or Mann-Whitney U test. Categorical data will be expressed as frequency (percentage) and compared using chi-square test or Fisher's exact test. Further data analyses may include: Kaplan-Meier survival curves; Log-rank test for differences; multivariate logistic regression and Cox regression with competing risks to assess predictive ability; ROC analysis to compare the diagnostic efficacy of the

new test with existing tests; subgroup analysis to assess effect modifiers; sensitivity analysis; interaction testing.

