2.1 Primary Objective

To conduct an epidemiological survey of hepatic encephalopathy in the Chinese population and further explore its diagnosis and treatment.

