2.2 Secondary Objectives

1. To investigate the diagnostic value of a newly developed mini-program for new-onset minimal hepatic encephalopathy and compare its efficacy with other tests; to explore whether long-term use of the new mini-program leads to differences in prognosis between patients who have experienced HE and those who have not; to evaluate patient and family compliance with and satisfaction towards the mini-program, as well as the feasibility of promoting this model in clinical practice; to assess the subsequent economic benefits of the mini-program...

2. To investigate the predictive value of the third lumbar skeletal muscle index (L3-SMI) for the prognosis of sarcopenia/frailty/malnutrition in the cirrhotic population...

3. To further evaluate the quality of life of patients with hepatic encephalopathy...

[etc...]

3. Study Design

This study is a prospective, multicenter cohort study. Cirrhotic patients and healthy individuals who meet the inclusion criteria will be recruited from outpatient clinics and inpatient wards. Baseline assessments will be completed, and relevant baseline data will be collected, including: demographic information, cirrhosis details (etiology, previous complications, prior hospitalizations or infections, medication use, TIPS), cirrhosis comorbidities, laboratory test results, imaging findings, results of various tests for hepatic encephalopathy, nutritional status, quality of life, physical measurements, etc. Grouping will be based on predefined endpoints. Different groups of participants will be followed up at month 1, 3, 6 after baseline, and then once every six months. At each follow-up, similar categories of data as baseline will be recorded. Finally, data will be integrated and analyzed, and validated in an external cohort.

4. Study Population

The study subjects are cirrhotic patients and healthy individuals. Recruitment will be conducted among patients attending hospital outpatient or inpatient departments who agree to follow-up. Enrolled individuals will be followed prospectively for 3 years. Patients are required to return for follow-up visits at 1, 3, and 6 months after their first outpatient visit or discharge, and then every six months thereafter. Follow-up will be conducted in person when patients return for visits.

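### Exclusion (3) makes undefined data completeness an eligibility condition, so HE prevalence and test accuracy are likely to describe only patients who completed the tests

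*Protocol*

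**What the plan says.** Section 4.2 excludes people with "3) Incomplete required data". The protocol does not say which data are required, when completeness is judged, or whether people removed on this ground are counted.

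Section 3 describes the design: "This study is a prospective, multicenter cohort study". People are recruited first; then "Baseline assessments will be completed, and relevant baseline data will be collected". Those data include "results of various tests for hepatic encephalopathy, nutritional status, quality of life, physical measurements, etc".

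Two objectives depend on who stays in:

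- Section 2.1, the primary objective: "To conduct an epidemiological survey of hepatic encephalopathy in the Chinese population and further explore its diagnosis and treatment".
- Section 2.2, first item: "To investigate the diagnostic value of a newly developed mini-program for new-onset minimal hepatic encephalopathy and compare its efficacy with other tests". The same item also asks about compliance, satisfaction and the feasibility of using the mini-program in practice.

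Section 5 says how selection bias is to be controlled: the eligibility criteria are to be clear and unified, and "participants will be enrolled through consecutive recruitment rather than convenience sampling".

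**The concern.** An eligibility criterion should be decidable before the study measurements are made. Under Section 3, whether the HE tests and other baseline items are complete is known only after they have been attempted. Read that way, the criterion is a deletion after assessment, placed in the eligibility list.

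This matters more here than in most cohorts. Section 1 describes HE as a spectrum that starts with mild cognitive impairment and ends in coma. A patient who cannot finish a cognitive test may well be one who has the condition. If so, the patients removed are not a random subset. The prevalence estimate and the accuracy of the mini-program would then refer to people able to complete everything, not to the patients recruited. The number who could not complete the mini-program is itself a feasibility finding, and the rule discards it.

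Consecutive recruitment protects against selection only if those recruited stay in the analysis. An undefined completeness rule weakens that protection, and it is hard to call it a clear criterion.

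**Working it through.** **The plan's own figures.** Section 6 gives sensitivity 0.667, specificity 0.595, W = 0.1 and prevalence 50–80%. With Z = 1.96:

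- Diseased: 1.96² × 0.667 × 0.333 / 0.1² = 85.3, rounded up to 86.
- Non-diseased: 1.96² × 0.595 × 0.405 / 0.1² = 92.6, rounded up to 93.
- At 50%: 86/0.5 + 93/0.5 = 358. At 80%: 86/0.8 + 93/0.2 = 572.5, rounded to 573.
- With 15% dropout: 358/0.85 = 421.2 and 573/0.85 = 674.1.

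These match the stated 358–573 and 421–674. The present point does not change them.

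**Assumption.** The protocol gives no rate of incomplete tests, overall or by disease status. I take 15% overall, borrowing only its size from the dropout allowance, and vary the split.

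**Prevalence.** Let p be the true prevalence, and m_d and m_n the incomplete shares among diseased and non-diseased. Among completers,

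observed = p(1 − m_d) / [p(1 − m_d) + (1 − p)(1 − m_n)].

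With 15% incomplete overall, the denominator is always 0.85.

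| True p | Split of the incomplete 15% | Observed |
|---|---|---|
| 50% | equal, 15% in each group | 0.425/0.85 = 50.0% |
| 50% | 25% of diseased, 5% of non-diseased | 0.375/0.85 = 44.1% |
| 50% | all incomplete are diseased | 0.35/0.85 = 41.2% |
| 50% | all incomplete are non-diseased | 0.50/0.85 = 58.8% |
| 80% | all incomplete are diseased | 0.65/0.85 = 76.5% |
| 80% | all incomplete are non-diseased | 0.80/0.85 = 94.1% |

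The error can run either way, and it vanishes when incompleteness is equal.

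**Accuracy.** Suppose the missing item is the mini-program and HE status is known from the reference test. Take the Section 6 values as the complete-case figures, with 15% incomplete in the group concerned. Counting non-completers as all negative or all positive gives these bounds:

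- Sensitivity: 0.667 × 0.85 = 0.567 (all negative) to 0.567 + 0.15 = 0.717 (all positive).
- Specificity: 0.595 × 0.85 = 0.506 (all positive) to 0.506 + 0.15 = 0.656 (all negative).

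The lower sensitivity bound is 0.10 below 0.667, a distance equal to the planned W. Recruiting more patients does not reduce it.

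**Direction of the accuracy effect.** Now assume that 30% of diseased and 10% of non-diseased patients do not complete the test.

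- Counted as positive: sensitivity 0.667 × 0.7 + 0.3 = 0.767; specificity 0.595 × 0.9 = 0.536; Youden's index 0.302.
- Counted as negative: sensitivity 0.667 × 0.7 = 0.467; specificity 0.595 × 0.9 + 0.1 = 0.636; Youden's index 0.102.
- Completers only: Youden's index 0.667 + 0.595 − 1 = 0.262.

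Whether completers make the test look better or worse depends on how non-completion is counted, which the protocol does not settle.

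**The case against.** The strongest defence is that the criterion may mean something narrower. It stands in an eligibility list, and Section 3 never calls the baseline items required. It could refer only to data needed to establish eligibility, such as the imaging, elastography or biopsy results used to diagnose cirrhosis. That reading is possible and would be largely harmless, but the protocol does not state it, so the ambiguity itself needs repair.

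Other criteria already remove some of the same patients: expert use of the mini-program, good compliance and full understanding, ability to consent, and the investigator's judgement of unsuitability. This stands. Criterion (3) adds to that selection and is not its only source, so deleting it will not remove all of it.

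Handling of missing data is commonly left to a statistical analysis plan, which is not shown here. That covers imputation and sensitivity analyses for enrolled people. It does not cover people whom the eligibility section takes out of the cohort, and the unspecified sensitivity analysis in Section 7 does not bring them back.

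Four stronger readings are tempting, and the protocol supports none of them:

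- That prevalence is understated. Impaired patients failing the tests would push it that way, but no incompleteness rates by disease status are given.
- That the new test is flattered. Under the 30% versus 10% assumption with non-completion counted as positive, only specificity is; sensitivity and Youden's index are higher than among completers.
- That sicker patients drop out of the prognosis analyses. Nothing says incomplete follow-up triggers exclusion, and the survival methods in Section 7 accommodate censoring.
- That the 15% dropout allowance conflicts with the criterion. It does not; it is an allowance for numbers and reproduces correctly.

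**Conclusion.** The point holds in a limited form. The protocol fixes an exclusion rule whose content and timing are undefined. Set beside the order of events in Section 3, its natural reading removes patients who could not complete the tests. Prevalence and accuracy are then likely to describe completers, a feasibility result is lost, and the safeguard in Section 5 is weakened.

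This conclusion rests on two assumptions: that the required data include the HE tests, which the protocol implies but does not state, and that non-completion is related to HE status or to the test result, which is plausible but not shown. The illustrated shift of up to 8.8 percentage points either way at a true prevalence of 50% is a limiting case under an assumed 15% incompleteness, not an estimate. Size and direction remain unknown.

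**What to change.** Delete exclusion (3), or replace it with a short, defined list of screening data that are available before any study test, for example those needed to establish cirrhosis.

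Then state that:

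- every consented, eligible patient stays in the cohort and is reported, with the reason for each incomplete test;
- test non-completion appears as its own row in the accuracy table;
- sensitivity analyses count non-completion once as positive and once as negative, so that the results show bounds.

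The last two items may sit in the statistical analysis plan; the change to eligibility belongs in the protocol. The cost is one line of protocol text, slightly more analysis work and wider reported uncertainty. The change is best made before anyone is excluded under the present wording, because data on those people may not be recoverable.

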A prospective cohort study on the epidemiological
investigation, diagnosis, and treatment of hepatic
encephalopathy

DATE: 16th May,2026

1. Research Background

Hepatic encephalopathy (HE) is a common and serious complication in the course of chronic liver disease and acute liver failure. It presents with a wide range of neuropsychiatric abnormalities, from subclinical changes (mild cognitive impairment) to obvious disorientation, confusion, and even coma. This not only significantly affects patients' quality of life and survival prognosis but also imposes a heavy burden on healthcare systems.

The incidence of HE is approximately 11.6 cases per 100 person-years. Among patients with cirrhosis, the prevalence of overt HE is 10-14%, increasing to 16-21% in those with decompensated cirrhosis, and 10-50% in patients undergoing transjugular intrahepatic portosystemic shunt (TIPS). The prevalence of minimal hepatic encephalopathy (mHE) ranges from 20% to 80%. China currently lacks national, multicenter epidemiological data on HE; in particular, the prevalence and disease outcomes of covert hepatic encephalopathy (CHE) need to be clarified.

Diagnosis of HE is also a major challenge. There remains a lack of definitive laboratory tests, and diagnosis mainly relies on exclusion. Although ammonia plays a key role in the pathophysiology of HE, studies have shown that blood ammonia cannot accurately identify HE, and there is no difference in lactulose treatment between patients with normal versus elevated ammonia levels. Currently, tools such as the Psychometric Hepatic Encephalopathy Score (PHES) are commonly used clinically, but their ability to predict overt HE (OHE) is limited by multiple factors. According to the West Haven criteria, HE is further classified into CHE and OHE. Research on CHE is relatively scarce, and many issues remain to be explored. First, diagnosing CHE is difficult. No laboratory method can diagnose or exclude it, and the diagnostic efficacy of existing tests for CHE requires further evaluation. Second, test performance is suboptimal; not all existing tests have undergone cross-sectional and longitudinal validation. Moreover, because cognitive ability is highly dependent on education and cultural environment, complex tests involving letter or math skills may show greater variability across different countries and cultures.

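### The cirrhosis sample size adds two terms that are each already a whole-cohort size, so it overstates N at both prevalences, and the target is then left as an unresolved range

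*Protocol*

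**What the plan says.** Protocol Section 6 computes the number of patients needed with HE from an anticipated sensitivity, and the number needed without HE from an anticipated specificity. It divides the first by the prevalence and the second by one minus the prevalence, and adds the results. The inputs are "The specificity was 0.595, sensitivity 0.667" and "The proportion of HE in the cirrhotic population is 50-80%, and W was set at 0.1". The totals are: "At a prevalence of 50%, the sample size was 358; at 80%, the sample size was 573". After inflation: "Assuming a dropout rate of 15%, approximately 421-674 cases are ultimately needed". The section does not say which end of that range governs enrolment. Healthy participants are sized separately, at 120.

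Two other places bear on the point. The bias-control paragraph at the end of Section 5 says that "participants will be enrolled through consecutive recruitment rather than convenience sampling". Section 1 states: "The prevalence of minimal hepatic encephalopathy (mHE) ranges from 20% to 80" per cent. Minimal HE is the condition that the mini-program in secondary objective 1 (Section 2.2) is meant to detect.

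**The concern.** Dividing the required number of diseased patients by the prevalence gives the size of the whole cohort that is expected to contain that many diseased patients. The remaining patients in that cohort are non-diseased and count towards specificity. The second term has the same meaning with the groups exchanged. Adding the terms would be right only if two separate cohorts were screened, one for each measure, and the patients of the other status were discarded. The protocol describes one cohort that supplies both groups.

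This calculation is the only basis given for the number of cirrhotic patients. If the combination rule is wrong, the stated totals are not what the stated precision requires. In addition, a target given as a range across an unknown prevalence does not tell the study which number secures the precision it claims.

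**Working it through.** **Inputs.** Sensitivity 0.667, specificity 0.595, W = 0.1, prevalence 0.50 to 0.80 and dropout 15%, all from Section 6. Z is not given for the diagnostic formula. I take 1.96, the value used for the healthy group ("with $Z=1.96$, $W=2$, and standard deviation=10"), and the reproduction below confirms it. W acts as a half-width.

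**Step 1: numbers per group**, n = Z² p(1 − p)/W².
- Diseased: 1.96² × 0.667 × 0.333 / 0.01 = 85.3, rounded up to 86.
- Non-diseased: 1.96² × 0.595 × 0.405 / 0.01 = 92.6, rounded up to 93.

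**Step 2: reproduce the protocol's totals with its sum.**
- 50%: 86/0.5 + 93/0.5 = 172 + 186 = 358.
- 80%: 86/0.8 + 93/0.2 = 107.5 + 465 = 572.5, rounded up to 573.
- Dropout: 358/0.85 = 421.2 and 573/0.85 = 674.1.

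All four figures reproduce. A one-sided Z (251 and 401) and W read as a full width (1423 and 2278) do not.

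**Step 3: replace the sum with the larger term**, N = max[n(diseased)/prevalence, n(non-diseased)/(1 − prevalence)].

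| Prevalence | Two terms | Sum | Larger term (evaluable) | Enrolled (÷ 0.85) |
|---|---|---|---|---|
| 20% | 430; 116.25 | 547 | 430 | 506 |
| 50% | 172; 186 | 358 | 186 | 219 |
| 80% | 107.5; 465 | 573 | 465 | 548 |

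The excess is 358/186 = 1.92, or +92%, at 50%, and 573/465 = 1.23, or +23%, at 80%. At the top of the range, 674 − 548 = 126 more patients are enrolled than W = 0.1 calls for.

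**Step 4: expected precision**, half-width = 1.96 × √[p(1 − p)/n in the group].

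| Evaluable | Prevalence | Diseased | Non-diseased | Sensitivity ± | Specificity ± |
|---|---|---|---|---|---|
| 358 | 20% | 71.6 | 286.4 | 0.109 | 0.057 |
| 358 | 50% | 179 | 179 | 0.069 | 0.072 |
| 358 | 80% | 286.4 | 71.6 | 0.055 | 0.114 |
| 465 | 20% | 93 | 372 | 0.096 | 0.050 |
| 465 | 80% | 372 | 93 | 0.048 | 0.0998 |
| 573 | 80% | 458.4 | 114.6 | 0.043 | 0.090 |

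**Step 5: where 358 evaluable stops being enough.** Specificity needs 93 non-diseased, so the limit is a prevalence of 1 − 93/358 = 0.74. Sensitivity needs 86 diseased, so the limit is 86/358 = 0.24. If all 421 enrolled were evaluable, the specificity half-width at 80% would still be 0.105.

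**The case against.** The strongest reply is that the sum can never be smaller than the maximum, so the formula can only err towards more patients. Each stated total more than meets W = 0.1 at the prevalence it was computed for. That is correct, and it limits the point. A reader might infer from the 0.114 above that the low end of the range simply fails its stated precision. The documents do not support this: 358 was derived for 50% prevalence, where it gives 0.069 and 0.072, and its excess is proportionately larger than that of the top end. The shortfall arises only if 421 is enrolled and prevalence turns out above about 74% or below about 24%. It comes from the unresolved range, not from the sum.

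It can also be said that the extra patients are not wasted, because the same cohort serves the epidemiological survey, the three-year follow-up and the prognostic models, while the diagnostic aim is secondary. This stands as a possible reason for a larger cohort, but Section 6 does not offer it.

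A further reply is that Section 6 speaks of HE and Section 1 of minimal HE, so 50–80% and 20–80% need not conflict. The mismatch deserves a sentence in the protocol, but it does not move the target: at 20% the larger term is 430, below the 465 already needed at 80%.

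Finally, 465 has no margin. At 80% prevalence it yields 93 non-diseased patients only on average, with about a 48% chance of fewer. If specificity were near 0.5, 93 patients would give 1.96 × √(0.25/93) = 0.102. This also stands, so 465 is a minimum in expectation and not a guarantee.

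**Conclusion.** The combination rule in Section 6 is wrong for a single consecutively recruited cohort, and it overstates N at both prevalences: 358 against 186 evaluable at 50%, and 573 against 465 at 80% (enrolled: 421 against 219, and 674 against 548). The protocol's arithmetic and dropout inflation are correct as applied; the fault is in adding the terms.

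Separately, no governing end is chosen for the range. Enrolling only 421 would be expected to miss W = 0.1 for specificity at prevalences above about 74%, which lies within Section 6's own 50–80%. It would miss for sensitivity below about 24%, which lies within the 20–80% that Section 1 gives for minimal HE. The misses are modest: 0.114 at 80% and 0.109 at 20%.

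These figures assume Z = 1.96, the protocol's anticipated sensitivity and specificity, 15% dropout, and group sizes at their expected values. Severity is moderate, because the formula error over-enrols and the precision risk depends on a particular choice of target and an extreme prevalence.

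**What to change.** In Section 6:

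1. Replace the sum with N = max[n(diseased)/prevalence, n(non-diseased)/(1 − prevalence)].
2. State one target in place of the range: at least 465 evaluable, about 548 enrolled with 15% dropout. Describe it as the minimum that meets W = 0.1 in expectation for both measures at prevalences from 20% to 80%.
3. Say which prevalence range applies to the condition the mini-program is to detect, and align it with Section 1.
4. If a larger number within the planned range is kept, as margin or for the other objectives, justify it on those grounds and report the precision it gives. For example, 573 evaluable at 80% prevalence gives about ±0.043 for sensitivity and ±0.090 for specificity.

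The cost is a rewrite of one section. The target of 548 lies inside the range already planned, so no patients beyond that range are needed.
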